#### **5.5.1.2. Analysis of Adverse Events**

Number and percentage of participants with at least one particular AE (unsolicited/solicited) will be tabulated. Unsolicited AEs will be summarized by System Organ Class and Preferred Term.

Solicited AEs will be summarized by class (administration site, systemic) and preferred term. AESI analyses will be summarized by Interest Category and Preferred Term.

For solicited AEs, the following tables will be provided: summary, by worst severity grade, at least grade 3, related (systemic only), time to onset (in days) and duration (in days). Note: Duration is defined as number of days from the start of the event until resolution of the event. The time to first onset is defined as (date of first onset – reference date + 1). The reference date is the start date of the post-dose period.

For unsolicited AEs following tables will be provided: summary table (including SAE, fatal outcome, potential AESI, AE leading to study discontinuation), all events, most frequent, at least grade 3, related, AE leading to study discontinuation, SAE, related SAE, potential AESIs qualified for assessment and potential AESI.

Moreover, table with Covid-19 related AEs, potential AESI as identified by the investigator, potential AESIs selected programmatically and potential AESI qualified for assessment will be created.

Potential AESIs selected programmatically will be tabulated by categories: '*Embolic and thrombotic events (SMQ)*' and '*Haematopoietic Thrombocytopenias (SMQ) (broad) or HLT = Thrombocytopenias*'. Potential AESI determined programmatically, related to study vaccine (investigator assessment), will be tabulated similarly.

Potential AESIs as identified by the investigator, will be tabulated by categories: '*Embolic and thrombotic events (SMQ)*' and '*Haematopoietic Thrombocytopenias (SMQ) (broad) or HLT = Thrombocytopenias*', and '*Other*'. Potential AESI as identified by the investigator, related to study vaccine (investigator assessment), will be tabulated similarly.

Potential AESIs qualified for assessment will be tabulated by categories: '*Embolic and thrombotic events (SMQ)*' and '*Haematopoietic Thrombocytopenia (SMQ) (broad) or HLT=Thrombocytopenias*'.

All AESI analyses will be presented by phase as well as by time interval. The definition of the different time intervals can be found in Section [5.1.2](#).

For AESI analyses, attribution to the intervals will be done similarly to the unsolicited AEs as described in Section [5.5.1.3](#). For Step 2 of phase allocation of adverse events, the '0 - 28 days post-dose' interval should be treated similar to 'active' periods and the rest as 'non- active' periods.

Listings and/or participant narratives will be provided as appropriate, for those participants who die, discontinue study due to an AE, or experience a severe or serious AE or potential AESIs.

### **5.5.1.3. Phase Allocation of Adverse Events**

As the analysis of solicited events will be based on the overall assessment of the investigator, which is documented in the CE domain, the Analysis Data Model (ADaM) dataset will be based

on the CE domain. Solicited events are allocated to the phases as described below, however they are always allocated to Post-dose period and will never be attributed to the screening phase. Time of day is not considered while attributing solicited AEs to phases.

For unsolicited AEs, the steps below are followed as well.

**Step 1: Allocation of events to the periods:**

Adverse events in the SDTM database are allocated to periods based on their start date/time. If the start date/time of an event falls between (or on) the start and stop date/time of a period, the AE is attributed to that period (treatment-emergent principle).

- In case of partial start or stop dates (ie time and/or day and/or month and/or year missing), the events are allocated to the periods using the available partial information on start and end date; no imputation will be done. If, for instance, the AE start date only month and year are available, these data are compared to the month and year information of the periods. This rule may lead to multiplication of the event as a consequence of its assignment to multiple periods.

- In case of a completely missing end date, the date is imputed by the cut-off date of the analysis for participants still ongoing in the study, and by the end date of the last period for participants who discontinued or completed the trial. The imputed end dates will not be shown in the data listings. In case of a completely missing start date, the event is allocated to the first active phase (Post-dose period), except if the end date of the AE falls before the start of the first active phase (Post-dose period).

**Step 2: Combination of events:**

Overlapping/consecutive events are defined as events of the same participant with the same preferred term which have at least 1 day overlap or for which the start date of an event is 1 day after the end date of the preceding event. Overlapping/consecutive events may be combined into one AE or not, according to the following rules:

- 1) If overlapping/consecutive events start in one of the following phases/periods - Screening or Follow-up (defined as non-active periods) - followed by an AE in - Post-dose period (defined as active period) - they are allocated to their respective phases/periods and are considered as separate events.
- 2) In case overlapping/consecutive events start within a single period, they are considered as one and the same AE. The individual events which contribute to this AE are retained as individual records in the ADaM database but are assigned the same onset, period, and total duration. All related attributes to the AE/phase/period should also be consistent with the new event.
- 3) In case overlapping/consecutive events start in both an active period followed by a consecutive non-active period, they are allocated to the active period only and are considered as one and the same AE. The individual events which contribute to this AE are retained as individual records in

the ADaM database but are assigned the same onset, treatment period, and total duration. All related attributes to the AE/phase/period should also be consistent with the new event.

4) In case an active period is followed by another active period, and the overlapping/consecutive events start in both periods, they are allocated to their respective period and are considered as separate AEs. In case overlapping/consecutive events start in non-consecutive periods (regardless of active or non-active), they are allocated to their respective period and are considered as separate AEs.

5) In case a non-active period is followed by another non-active period, and the overlapping/consecutive events start in both periods, they are allocated to the first period and they are considered as one and the same AE. The individual events which contribute to this AE are retained as individual records in the ADaM database but are assigned the same onset, period, and total duration. All related attributes to the AE/phase/period should also be consistent with the new event.

Remarks:

1. Events can only be combined into one and the same AE if their start and stop dates are known.
2. In case the completely missing end date is imputed (for period allocation), this date is also considered as a complete date.
3. Time is not considered when determining overlap of events.

#### **5.5.1.4. Missing Data**

Missing data will not be imputed. Participants who do not report an event will be considered as participants without an event. An AE with a missing severity or relationship will be considered as an AE reported, but will be considered as not reported for the severity or relationship. For example, an AE with missing severity will be considered as an AE reported for the analysis of any grade but will be considered as not reported for the analysis of at least grade 3. The analysis of solicited AEs will include the safety data as documented by the investigator.

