**5.7.1. Data Monitoring Committee (IDMC) or Other Review Board**

An Independent DMC (IDMC) will be installed to monitor the safety of participants in the ongoing VAC18193 Phase 3 studies.

There are no planned IDMC reviews in the current study. Safety issues that might arise from this study may be escalated to an IDMC.

If a safety issue arises, the team might request an ad hoc safety review by the IDMC. This review would be based on a snapshot of the database which might not have been completely cleaned. Data will be cleaned on an ongoing basis. The IDMC will review unblinded data; the data package to be reviewed (summary data) will display the real vaccine identity. The study team will transfer the blinded data to the statistical support group (SSG), and the IWRS vendor or Secure Data vendor will securely transfer the unblinded randomization data to the SSG. In principle there will be no meeting unless this is requested by one of the IDMC members or by the Sponsor.

Conclusions from the IDMC reviews will be communicated to the Sponsor.

The IDMC data package (summary data) will follow the same statistical methods described in this SAP. Depending on the safety issue, the IDMC data package will consist of one or more of the following tabulations: participant disposition and demographics, SAEs, related SAEs, fatal AEs, related fatal AEs, solicited and unsolicited grade 3 AEs and related AEs. Potential AESIs qualified for assessment and potential AESI will be listed. Other safety summaries might be requested as well. A separate IDMC DPS document will be provided to describe the specifications of the individual tables to be generated should a safety issue arise.

Data packages will be distributed by the SSG to the IDMC members via a secure electronic environment. A separate data package might be made available to the study team where the summary data are presented for the pooled groups (blinded).

The roles and responsibilities of the IDMC and SSG are detailed in Section 5 of the IDMC charter.

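### AEs with a missing relationship or severity leave the related and at-least-Grade-3 tables without any missing count, which matters mainly for an ad hoc IDMC package

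*SAP*

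**What the plan says.** SAP 5.5.1.4 opens with "Missing data will not be imputed". An AE with a blank severity or relationship is kept as an AE, "but will be considered as not reported for the severity or relationship". The SAP's worked example is an AE with missing severity: it enters the any-grade analysis but "will be considered as not reported for the analysis of at least grade 3". The same sentence covers relationship, so an AE with a blank relationship is absent from the related tables.

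SAP 5.5.1.2 plans the tables that this rule reaches: at least grade 3, related, related SAE, and potential AESIs related to study vaccine. It mentions no row, footnote or count for missing values and no sensitivity rule.

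SAP 5.7.1 carries the rule further. If a safety issue arises, the team may ask the IDMC for an ad hoc review. "This review would be based on a snapshot of the database which might not have been completely cleaned", although "Data will be cleaned on an ongoing basis". On methods it says: "The IDMC data package (summary data) will follow the same statistical methods described in this SAP". Besides disposition and demographics, the candidate tabulations are "SAEs, related SAEs, fatal AEs, related fatal AEs, solicited and unsolicited grade 3 AEs and related AEs". The package will hold one or more of these, depending on the issue. Potential AESIs are to be listed.

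**The concern.** A related-SAE table is read as the set of serious events that the investigator attributes to the vaccine. Under the stated rule, an SAE absent from it may have been judged not related, or may not have been judged at all. The table does not say which. The at-least-Grade-3 table has the same ambiguity.

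The direction is also one-sided: a blank can only lower these counts. Two nearby rules in the SAP go the cautious way. Under 5.5.2, a vital-sign abnormality with a missing baseline is always treated as emerging. Under 5.5.1.3, an AE with no start date goes to the post-dose period unless its end date precedes vaccination. Caution is not a uniform principle in the SAP, because Appendix 5 treats a therapy with no start date as having begun before the study. Still, causality and severity are the attributes that matter most for a safety signal, and here the default lowers the count.

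At stake is how the IDMC reads a small table in the one setting where it would be consulted. The primary comparison is not at stake.

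**Working it through.** The documents give no figure for missing severity or relationship, so there is nothing of the plan's own to reproduce. The check has two parts.

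**1. Following one event through the text.** Take an SAE with the relationship still blank at the snapshot.

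- All-AE table: included (SAP 5.5.1.4).
- All-SAE table: included, since that table does not filter on relationship. In an IDMC package this holds only if the table is supplied, because SAP 5.7.1 commits to one or more of the candidate tabulations.
- Related-AE and related-SAE tables: absent (SAP 5.5.1.4).
- Marker that a value is missing: none specified.

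For an AE with a blank grade, the at-least-Grade-3 table takes the place of the related tables and the result is the same.

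**2. Size, under assumptions.** Let k be the number of SAEs that the investigator would attribute to the vaccine once assessed. Let m be the probability that the relationship is blank for each at the snapshot, independently between events. Both k and m are assumed.

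P(at least one absent from the related-SAE table) = 1 - (1 - m)^k

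| k | m = 5% | m = 10% | m = 20% |
|---|---|---|---|
| 1 | 1 - 0.95 = 5% | 1 - 0.90 = 10% | 1 - 0.80 = 20% |
| 3 | 1 - 0.95^3 = 14% | 1 - 0.90^3 = 27% | 1 - 0.80^3 = 49% |
| 5 | 1 - 0.95^5 = 23% | 1 - 0.90^5 = 41% | 1 - 0.80^5 = 67% |

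The expected number still shown is k(1 - m). With k = 5 and m = 20% it is 5 × 0.80 = 4.0, so on average one event of five is absent.

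The planned group size is 120 (Protocol 4.1, Table 2). One event is 1/120 = 0.8% of a group, so a single omission can take a group's related-SAE count from 1 to 0.

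**The case against.** The case for leaving the rule alone has real substance.

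- **The event does not vanish.** It stays in the all-AE table and, if serious, in the all-SAE table. SAP 5.5.1.2 also provides listings or narratives, as appropriate, for deaths and for severe or serious AEs. This stands for the main analysis. It is weaker for the IDMC: the all-SAE table is not guaranteed and only potential AESIs are promised as a listing, though other summaries may be requested. For a non-serious event, selection as severe needs a grade, which is what is missing.
- **Blanks should be rare.** Protocol 10.2.5 obliges the investigator to record relationship. Protocol 8.3.1 requires SAE forms to be completed, reviewed by a physician and sent within 24 hours. Protocol 10.2.3 has all AEs graded, and derives erythema, swelling and fever grades from measurements. Solicited local AEs are related by definition. This stands, and it is why the effect at database lock should be small.
- **The setting is contingent.** No IDMC review is planned, cleaning is ongoing and safety is descriptive. This also stands, and it limits the importance of the point.
- **A missing row may be specified elsewhere.** The separate data presentation specifications might contain one. They are not among the documents, and nothing in the SAP requires it.

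A reader might infer that the SAP classifies unassessed events as not related. It does not: it treats the attribute as not reported and plans no not-related table. The lower related count is the same, but the classification is not there. A reader might also infer that the events which trigger a review are the ones most likely to be blank. That is plausible, but the documents offer no support for it.

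**Conclusion.** The rule is explicit, and its effect on the related and at-least-Grade-3 tables follows directly from it. Those tables can undercount without showing it. At final lock the undercount should be small. The point matters mainly for an ad hoc IDMC package, where the snapshot may not be fully clean and the all-SAE table may not accompany the related one.

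The size rests wholly on the assumed k, m and independence: 5% to 20% for one related SAE and 23% to 67% for five, with m from 5% to 20%. These figures apply only if k counts SAEs that would be judged related. If five SAEs of any cause were in the snapshot, the same arithmetic would give only the chance of some blank field. It would be wrong to read that as the chance that a related SAE is lost, because a blank on an event later judged not related causes no undercount.

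This is a worthwhile correction to safety reporting. It does not touch the non-inferiority analysis or the sample size.

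**What to change.** **SAP 5.5.1.4.** Count a missing relationship as related in the related-AE, related-SAE, related-fatal-AE and related potential-AESI tables, with a footnote giving the number so handled. Show missing severity as its own row or count beside the at-least-Grade-3 results, without recoding it. Recoding every blank grade as Grade 3 or higher could turn mild events into severe ones in already small counts. The all-SAE and all-fatal tables need no change, since they filter on neither attribute.

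**SAP 5.7.1.** Require the missing rows or counts in any IDMC package, and always supply the all-SAE table with the related-SAE table.

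**Cost.** A few sentences in the SAP and a programming flag. The downside is a small over-count of related events until queries are resolved. That over-count is visible in the footnote and reverses as the fields are completed, whereas an undercount under the present rule is not visible in the table.

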#### **5.5.2. Vital Signs**

Baseline and emerging vital sign abnormalities will be listed based on the abnormality gradings in [Appendix 6](#). An abnormality will be considered as emerging if it is worse than the baseline value. If the baseline is missing, the abnormality is always considered emerging.

### **5.6. Other Analyses**

#### **5.6.1. Definition of Subgroups**

No subgroup analysis is planned for this study.

### **5.7. Interim Analyses**

There is no interim analysis planned before the primary analysis.

**5.7.1. Data Monitoring Committee (IDMC) or Other Review Board**

An Independent DMC (IDMC) will be installed to monitor the safety of participants in the ongoing VAC18193 Phase 3 studies.

There are no planned IDMC reviews in the current study. Safety issues that might arise from this study may be escalated to an IDMC.

If a safety issue arises, the team might request an ad hoc safety review by the IDMC. This review would be based on a snapshot of the database which might not have been completely cleaned. Data will be cleaned on an ongoing basis. The IDMC will review unblinded data; the data package to be reviewed (summary data) will display the real vaccine identity. The study team will transfer the blinded data to the statistical support group (SSG), and the IWRS vendor or Secure Data vendor will securely transfer the unblinded randomization data to the SSG. In principle there will be no meeting unless this is requested by one of the IDMC members or by the Sponsor.

Conclusions from the IDMC reviews will be communicated to the Sponsor.

The IDMC data package (summary data) will follow the same statistical methods described in this SAP. Depending on the safety issue, the IDMC data package will consist of one or more of the following tabulations: participant disposition and demographics, SAEs, related SAEs, fatal AEs, related fatal AEs, solicited and unsolicited grade 3 AEs and related AEs. Potential AESIs qualified for assessment and potential AESI will be listed. Other safety summaries might be requested as well. A separate IDMC DPS document will be provided to describe the specifications of the individual tables to be generated should a safety issue arise.

Data packages will be distributed by the SSG to the IDMC members via a secure electronic environment. A separate data package might be made available to the study team where the summary data are presented for the pooled groups (blinded).

The roles and responsibilities of the IDMC and SSG are detailed in Section 5 of the IDMC charter.

## 6. SUPPORTING DOCUMENTATION

### 6.1. Appendix 1 List of Abbreviations

ADaM	Analysis Data Model
AE	adverse event
AESI	adverse event of special interest
ANOVA	Analysis of Variance
ATC	anatomic and therapeutic class
BCC	Brighton Collaboration Case Definition
BMI	body mass index
CDC	Center for Disease Control and Prevention
CI	confidence interval
CRF	case report form
CTM	clinical trial material
CTP	clinical trial protocol
DMC	Data Monitoring Committee
ECG	electrocardiogram
ELISA	enzyme-linked immunosorbent assay
ELISpot	enzyme-linked immunospot
FAS	full analysis set
FDA	Food and Drug Administration
FOIA	Freedom of Information Act
GMC	geometric mean antibody concentration
GMT	Geometric Mean Titer
ICF	informed consent form
ICS	intracellular cytokine staining
IDMC	Independent Data Monitoring Committee
IWRS	interactive web response system
LLOQ	lower limit of quantification
NA	not applicable
PPI	per protocol immunogenicity analysis set
PRAC	Pharmacovigilance Risk Assessment Committee
Pre F	prefusion conformation-stabilized F protein
RSV	respiratory syncytial virus
SAE	serious adverse event
SAP	Statistical Analysis Plan
SD	standard deviation
SDTM	Study Data Tabulation Model
SE	standard error
ULOQ	upper limit of quantification
VNA	virus neutralization assay
WHO	World Health Organization

## **6.2. Appendix 2 Changes to Protocol-Planned Analyses**

No changes to planned analysis.

### 6.3. Appendix 3 Demographics and Baseline Characteristics

The following demographic and baseline characteristics will be summarized.

**Table 6** presents a list of the demographic variables that will be summarized by vaccine regimen and overall, for the FAS.

**Table 6: Demographic Variables**

Continuous Variables:	Summary Type
Age (years)	Descriptive statistics (N, mean, standard deviation, median and minimum and maximum).
Weight (kg)	
Height (cm)	
Body Mass Index (BMI) (kg/m2)	
Categorical Variables:	
Sex (male, female, unknown, intersex)	
Race a (American Indian or Alaska Native, Asian, Black or African American, Native Hawaiian or other Pacific Islander, White, Multiple)	
Ethnicity (Hispanic or Latino, not Hispanic or Latino)	Frequency distribution with the number and percentage of participants in each category.
BMI ( <18.5 kg/m2 (underweight), 18.5-24.9 kg/m2 (Normal or Healthy Weight), 25-29.9 kg/m2 (Overweight), $\geq 30$ kg/m2 (Obese) )	
Risk level of severe RSV disease (Increased risk / Non-increased risk) as collected (CDC definition)	
COVID vaccination b at baseline (AstraZeneca COVID-19 vaccine, Janssen COVID-19 vaccine, Moderna COVID-19 vaccine, Pfizer COVID-19 vaccine, Other COVID-19 vaccine, No COVID-19 vaccination)	

a If multiple race categories are indicated, the Race is recorded as 'Multiple'

b Subjects can have taken multiple vaccinations, categories are not mutually exclusive.

#### **6.4. Appendix 4 Protocol Deviations**

Major protocol deviations will be summarized.

In general, a list of major protocol deviations that may have the potential to impact participants' rights, safety or well-being, or the integrity and/or result of the clinical study will be specified in a major protocol violation criteria document. Participants with major protocol deviations will be identified prior to database lock and the participants with major protocol deviations will be summarized by category. In addition, minor and major protocol deviations related to COVID-19 will be tabulated.

